5.3 Follow Up

Participants will be seen one week after the second day of the FMT or placebo dose, and then monthly for 6 months (1 month, 2 months, 3 months, 4 months, 5 months, 6 months), at 9 months and at 12-months after FMT or placebo (see Section 10, Study Calendar). Subjects who receive

FMT or placebo as outpatients will receive a phone call at 24-48 h after the second FMT or placebo dosing day. Standard physical exam, vitals, KPS, blood testing (CBC and chemistries), interval history, and GVHD assessment will take place at each study visit along with research toxicity assessments. Additionally, stool and urine samples for correlative studies will be collected at the 1 week, 1 month, 2-month, 6-month and 12-month follow-up visits.

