5. TREATMENT PLAN

5.1 Treatment Regimen

There will be two treatment arms. Arm 1 participants will receive **two doses of FMT after HCT**. Arm 2 participants will receive placebo capsules instead of FMTs at the same time points. Participants will be randomized in a 1:1 ratio. Double-blinding will be maintained.

An individual not involved in patient assessments will receive the randomization assignment, take appropriate capsules (either FMT (Arm 1) or placebo (Arm 2)) from relevant freezer locations, and place them on dry ice for administration. Vials will be labeled “STUDY Caps” for administration so that neither physician, research nurse, nor participant will be able to identify FMT vs. placebo capsules. The **certificate of analyses** identifying capsules as FMT or placebo will then be sealed in an opaque envelope and saved for review at the time of unblinding. This will serve as a “double-check” on actual assignment.

A total of 48 evaluable patients will be randomized between the FMT arm and the placebo arm (24 evaluable patients per arm).

Arm 1 will consist of **two (2)** doses of FMT **given after HCT**, starting within 4 weeks after engraftment after HCT.

Arm 2 will mirror Arm 1, using placebo capsules instead of FMT capsules. It will consist of **two (2)** doses of placebo, starting within 4 weeks after engraftment after HCT.

In this protocol, a standard dose of oral FMT will be defined as 15 capsules administered during on a single day. Thus 2 doses of FMT will total 30 capsules. In our previous study of FMT in patients undergoing allogeneic HCT, thirty capsules contained microbial content of a median of 38.6 g of feces (range, 24-56.7).

The FMT/placebo doses can be given within 4 weeks after engraftment after HCT. These 2 doses of oral FMT/placebo will be administered as 15 capsules per day for two days (total 30 capsules); the two days must occur within a **14** -day span – they can be consecutive, but they do not need to be.

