The doses of FMT or placebo will commence only after neutrophil engraftment has occurred, **defined as** $\text{ANC} \geq 500/\mu\text{L}$ for three (3) consecutive days. If the patient does not experience successful neutrophil engraftment, then the participant will not receive the second dose of FMT or placebo.

FMT/placebo **administration** must begin no later than 4 weeks after the date of neutrophil engraftment.

If the participant receives the first FMT placebo and then develops an infection requiring antibiotics, then the second dose of **FMT/placebo** will be delayed until 48 hours after the end of antibiotic dosing. In cases of infection requiring antibiotics, FMT or placebo must start within 2 weeks after stopping systemic antibiotics. Treatment with anti-viral agents, anti-fungal agents and/or trimethoprim / sulfamethoxazole is allowed at any time with no impact on FMT or Placebo administration.

A minimum of 15 (out of the usual total number of 30) capsules must be swallowed for a dose of FMT or placebo to be considered successful.

Subjects receiving any amount of FMT or placebo capsules will be followed for at least 6 months.

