6. DOSING DELAYS/DOSE MODIFICATIONS

If a participant has a difficult time swallowing 15 capsules in one day, then capsule administration may be spaced out over three (3) days (10 capsules per day), instead of the standard dosing over two (2) days (15 capsules per day). This is a standard approach in capsule based FMT for recurrent *C. difficile* colitis, though it is noted that the vast majority of patients, including children and the elderly, are able to take 15 capsules in a single sitting. There will be no dose adjustment for participants unable to take 10 capsules per day. In the case of a dosing delay or dose modification, dosing and assessment schedules will remain unchanged (i.e., dosing day count will continue).

Administration of the capsules with applesauce or pudding rather than water is also a standard approach, for subjects who have difficulty swallowing large capsules. The capsules are size 00 (the size of a large pre-natal vitamin). Please note that subjects are fasting around the time of administration to minimize the risk and volume of potential emesis, which is rare. There is no reason food would alter the efficacy of FMT.

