7.1 Expected Toxicities

In prior experiences, participants undergoing Fecal Material Transplantation experienced 24 – 48 hours of mild transient adverse events. Common events include fever, cramping, diarrhea, and gas.

Rarely participants experience bacteremia after FMT. In our institutional experience with over 400 FMT recipients (various clinical indications), there was a single incident where 2 subjects developed bacteremia from a relatively resistant organism (ESBL *E. coli*) that was later identified in the stool specimen from the same healthy FMT donor. This donor provided samples before specific screening for ESBL organisms was implemented. Additional screening will minimize this risk, but we don't believe it can be entirely eliminated.

Based on our previous experience with these subjects, special attention will be given to patients who develop bacteremia with enteric organisms within 4 weeks of FMT dosing and additional testing may be performed to assist with assessment of attribution.

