Done at the time of the first and last donations	Viral Loads
	Epstein-Barr virus
	Cytomegalovirus
Optional – done at screening	Oral Glucose Tolerance Test – Optional
	Glucose (fasting)
	Hemoglobin A1C
	Glucose tolerance test, 2 hours post glucola ingestion

Appearance

Exemplary capsules are shown below.

Storage

Capsules are frozen and stored at -80°C and shipped on dry ice. A dated certificate of analysis which includes lot number, and manufacture date, acceptance of donor testing, and structural integrity of capsules at the time of shipment or in person delivery on dry ice to an investigator for a specific recipient will be filed. It is recommended that capsule be stored no longer than 30 days at -20°C, in a FROST-FREE freezer. Capsules should be discarded 9 months after manufacture. Capsules should be promptly transported on dry ice once removed from the freezer, for administration to subjects.

Animal testing

No animal testing has been performed on FMT capsules.

Solubility

FMT capsules and prototypes with aqueous dyes are demonstrated to be relatively stable in an acid environment and release payload under neutral conditions. It is

therefore NOT required nor recommended that subjects take antacids, bicarbonate or other acid-suppressing medications prior to administration. Taking these medications are not contraindications to administration of FMT capsules however.

Instructions for Use

Subjects must meet study-specified inclusion and exclusion criteria. Subjects should be NPO for 4 hours prior to and one hour after administration of capsules.

For treatment of *C. difficile* infection (CDI)

A single dose is considered 30 capsules when treating CDI. Capsules may be administered on 2 successive days (15 each day) or 3 successive days (10 each day), at the choice of subject/physician. For simple convenience most people prefer 2 days. Subjects or parents should sign a clinical consent form. Follow-up phone calls and completion of the 2-sided follow-up Case Report Form provided are required at the following intervals

- in the 24-96 hours window after administration
- at 7-14 days
- at 8 weeks (+/- 5 days)
- at 6 mo (+/- 2 weeks)

and subjects should be seen in person as dictated by a physician's clinical judgment. Physicians who do not complete and return follow-up forms in a timely manner will not be provided additional capsules.

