For other applications, doses will be defined within specific clinical protocols, but will generally follow the above timing for safety assessments.

Acute reactions after dosing in 403 subjects treated for *C. difficile*

The capsules are tasteless and odorless. Five adult subjects and two children of 403 total have vomited within 8-12 h after capsule administration and **not** brought up feculent material or intact capsules. One cancer patient with chronic vomiting of medications vomited up all 15 capsules of his second dose, after tolerating the first dose well. Diarrhea and irritable bowel-like symptoms are commonly reported after FMT for CDI and often resolve over time. Subjects may be discharged after explanation of follow-up and advised re diet, relapse and AE's to monitor which usually takes about 20 minutes.

Total Adverse Events in 395 subjects reaching 8 weeks follow-up

Most subjects treated for CDI have some ongoing GI symptoms, typically minor (Grade 1). It is impossible to determine if these symptoms are related to resolving CDI, post-infectious irritable bowel syndrome, or the capsules themselves. See Chart 1 below. One IBD flare requiring intensified treatment has been noted and deemed related.

EVENT	Number	Percentage
Fevers - transient	9	3%
Hospitalizations	44	16%
Deaths	24	8%

Diarrhea	145	48%
Nausea/bloating	78	25%
Ulcerative colitis flare	3	0.01%

Expected resolution of symptoms of *C. difficile*.

This is variable. The occasional individual has fever, cramping, borborygmi and occasional diarrheal bowel movements after dosing. Patients with significant abdominal pain as part of their presenting or ongoing symptoms may have a component of Irritable Bowel Syndrome. Episodic pain or nonspecific abdominal discomfort may persist. Some subjects resolve diarrhea but have ongoing frequent formed stools compared with baseline. In the MGH experience, some subjects have cleared stool of *C. difficile* based upon repeated testing, but had slow resolution of other symptoms over weeks. Cure is defined as resolution of diarrhea at 8 weeks (3 stools or less per day).

Definition of Relapsed CDI

A relapse qualifying for re-dosing must meet the following criteria:

- Relapsed or ongoing diarrhea (more than 4 bowel movements of Bristol Grade 3 or higher AND
- A positive stool test for *C. diff* (toxin or PCR) on day 5 or later (Day 0 = initial dose day). Routine rescreening of stools in the absence of significant symptoms is not recommended.

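### Outpatients dosed three or more days apart, or on one day only, have no scheduled safety contact 24-48 h after the first dose

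*Combined protocol and SAP*

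**What the plan says.** **The call and the first visit.** Under Section 5.3, participants who receive "FMT or placebo as outpatients will receive a phone call at 24-48 h after the second FMT or placebo dosing day". The 1-week visit is also counted from the second dosing day. The Section 10 calendar marks AE evaluation on Day 1, on Day 2 and at one week after the second dose. It has no column between Day 1 and Day 2 and no entry for the call.

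**Spacing.** Section 5.1 gives 15 capsules on each of two days: "the two days must occur within a 14 -day span – they can be consecutive, but they do not need to be". If an infection needs antibiotics after the first dose, the second "will be delayed until 48 hours after the end of antibiotic dosing".

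**Incomplete or extended dosing.** Section 5.5 lists reasons why a participant may not receive every dose. Section 9.2 says that, without a second day, later sample collections are counted from the first. Section 10, note (H), counts the monthly visits from the last dose. Neither mentions the call or the 1-week safety visit. Under Section 6, "capsule administration may be spaced out over three (3) days (10 capsules per day"), with the assessment schedule left as it was.

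**Reaction period.** Section 7.1 reports that earlier recipients "experienced 24 – 48 hours of mild transient adverse events", and names fever, cramping, diarrhea and gas.

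**The concern.** The call appears designed to catch the short reactions of Section 7.1 in patients who have gone home. With consecutive dosing days, a call after the second day is enough, because the Day 2 visit covers the first dose. Section 5.1 does not require consecutive days, and Section 5.5 means that some patients have no second day. For those outpatients the call is either long past the reaction period of the first dose or is never triggered.

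What is at stake is the record of early tolerability after the first exposure to donor material. A reaction that lasts a day or two at home is recorded only if the patient reports it unprompted or remembers it later. Fever within 48 hours before dosing also bars that dose under Section 5.2. A reaction to the first dose could therefore be one reason why the second day, and with it the call, does not occur.

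**Working it through.** The plan states no figure for this interval, so the check is a day count.

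**Inputs**
- Call: 1-2 days after the second dosing day, outpatients only (Section 5.3).
- 1-week visit: 7 ± 3 days after the second dosing day (Section 5.3; Section 10, note (I)).
- Two dosing days within a 14-day span (Section 5.1).
- Reaction period: 24-48 h (Section 7.1), assumed to begin soon after dosing.
- Day 2 is an in-person visit with examination, laboratory tests and AE evaluation (Section 10).

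**Formulas.** Let g be the number of days from the first dosing day to the second. Counted from the first dose:
- Day 2 visit: day g.
- Call: day g + 1 to g + 2.
- 1-week visit: day g + 7 ± 3, that is g + 4 to g + 10.

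The longest gap is 14 − 1 = 13 days if both dosing days count within the span, or 14 if the span is elapsed time.

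| g | Day 2 visit | Call | 1-week visit | Scheduled contact by 48 h after dose 1? |
|---|---|---|---|---|
| 1 | day 1 | day 2-3 | day 5-11 | yes |
| 2 | day 2 | day 3-4 | day 6-12 | yes, just |
| 3 | day 3 | day 4-5 | day 7-13 | no |
| 13 | day 13 | day 14-15 | day 17-23 | no |
| 14 (elapsed reading) | day 14 | day 15-16 | day 18-24 | no |

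The Day 2 visit falls within 48 hours only at g = 1 or 2. That leaves g = 3 to 13, which is 11 of the 13 allowed gaps (12 of 14 on the elapsed reading). This counts permitted schedules, not patients. When the gap is long, the fever check before the second dose does not help, because it looks back only 48 hours.

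**One dosing day only.** No second day exists, so no call is defined. Section 9.2 moves the 1-week sample to 7 ± 3 = day 4-10 after the first dose. Section 5.3 says those samples are taken at the 1-week visit, so the visit probably moves with them, although the text does not say so. If it did not move, the first visit tied to dosing would be month 1, at 30 ± 14 = day 16-44. Both readings miss 24-48 h.

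**Three-day dosing.** If the days are consecutive, the call falls on day 2 + 1 to 2 + 2, that is dosing day 3 or 4. Counted from the last dose it would be day 4 or 5. The difference is one day.

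**Antibiotic delay.** Section 5.1 does not say whether the 14-day span still applies when an infection delays the second dose. The two statements need to be reconciled. Until they are, 13 days is the limit from the span rule alone.

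**The case against.** Much can be said for the plan as written, and most of it narrows the point.

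- **Most cover is already there when doses are close.** A reader might infer that the first dose never has early follow-up. The documents do not support that: at gaps of 1-2 days the Day 2 visit provides it, and inpatients do not depend on the call.
- **A one-day patient is probably seen at day 4-10.** A reader might infer a wait until day 16-44. That requires separating the 1-week sample from the visit at which Section 5.3 says it is collected, which is the less natural reading.
- **A reaction that stops dosing is already known.** If a patient comes off treatment for an unacceptable adverse event, Section 5.5 requires the reason and date on the case report form. That event is not found late. What can be missed is a milder reaction in a patient who stops for another cause.
- **Serious infection is a separate matter.** A reader might infer that bacteremia would be detected late. Section 7.1 sets a 4-week watch for enteric bacteremia, of which a 24-48 h call covers little. Section 11.3 collects infection data continuously, Section 5.4 provides for evaluation of febrile participants, and Section 7.3.1 requires SAE reporting from the initial dose.
- **Appendix B does not require a call per dose.** Its contact "in the 24-96 hours window after administration" follows capsules given on successive days as one treatment. Its remark that other protocols "will generally follow the above timing for safety assessments" is general.
- **Section 6 deliberately leaves assessments unchanged** under three-day dosing, and the effect there is about a day.

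All of this stands. What remains is that none of these safeguards is a scheduled, prompted contact at 24-48 h after the first dose for an outpatient with separated or single dosing. Blood draws for the GVHD biomarkers may bring some patients in, but they are timed from transplant, are not AE assessments, and are waived for patients co-enrolled in the biorepository protocol.

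**Conclusion.** The point holds in a limited form. For outpatients whose dosing days are 3 to 13 days apart, or who receive only one, the plan schedules no safety contact in the 24-48 h after the first dose. Mild reactions then depend on unprompted report or on recall. With two doses, recall is at the Day 2 visit, 3 to 13 days later. With one, it is at the 1-week visit, about day 4-10 if that visit moves with the samples.

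This assumes whole-day counting, both dosing days counted within the 14-day span, and reactions that begin soon after dosing. The documents do not give the share of patients treated as outpatients, on separated days or on one day only, so the number affected is unknown.

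A reader might infer biased safety or efficacy results. The documents do not support that: both arms follow the same schedule, the primary endpoint is urinary 3-IS at one month, and adverse event rates are not a listed secondary objective. This is an inexpensive improvement to safety data collection, not a flaw in the trial's main comparison.

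**What to change.** In Section 5.3 and the Section 10 calendar:

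1. Tie the existing 24-48 h outpatient call to each dosing day that is not followed by a study visit within 48 hours.
2. Anchor the 1-week safety visit to the last dosing day actually received, so that it is defined for one-day, two-day and three-day dosing.
3. List the call in the calendar as an AE contact, so that it is recorded.
4. Reconcile Sections 5.1, 5.3, 5.5, 6, 9.2 and 10 on which day anchors each assessment. State also how the 14-day span and the antibiotic delay in Section 5.1 fit together.

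The cost is about one extra phone call by existing staff for some outpatients, plus amendment wording. The contact and calendar changes in items 1-3 leave doses, dosing days and treatment rules as they are. Item 4 asks only that the text be made consistent.

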5.4 General Concomitant Medication and Supportive Care Guidelines

There are no required concomitant medications in this trial. Any concomitant medication administration is per the discretion of the treating physician(s). Participants may receive all concomitant therapy deemed necessary to provide optimal support.

Rarely, recipients of FMT have experienced fever after administration of FMT capsules. This is more common in younger individuals and children, and may represent an immunological reaction to a new intestinal flora. Participants who are febrile after FMT will have a clinical evaluation. Blood and other cultures will be performed as deemed clinically necessary. Such patients may be given antibiotics if they are hemodynamically unstable or clinically or microbiologically diagnosed with an active infection. Otherwise, it is recommended that they be observed.

Patients are allowed to be treated with any standard regimens for GVHD prevention as well as any post-HSCT therapies considered standard by the treating physician. Participants will not be allowed to be on any other investigational treatment protocol from admission for HCT until the final FMT vs placebo administration.

5.5 Criteria for Taking a Participant Off Protocol Therapy

After the second FMT or placebo administration (after HCT), the participant will be off protocol therapy. No further protocol therapy will be given.

A participant may not receive all doses of FMT or placebo if any of the following criteria applies:

- Intercurrent illness that prevents further administration of treatment
- Unacceptable adverse event(s)
- Participant demonstrates an inability or unwillingness to comply with the regimen
- Participant decides to withdraw from the protocol therapy
- General or specific changes in the participant's condition render the participant unacceptable for further treatment in the judgment of the treating investigator

Participants will be removed from the protocol therapy when any of these criteria apply. The reason for removal from protocol therapy and the date the participant was removed must be documented in the case report form (CRF). Alternative care options will be discussed with the participant.

When a participant is removed from protocol therapy and/or is off of the study, the relevant Off-Treatment/Off-Study information will be updated in OnCore.

5.6 Duration of Follow Up

Participants will be followed for 12 months after the last day on which he/she received FMT or placebo capsules or until death, whichever occurs first.

5.7 Criteria for Taking a Participant Off Study

Participants will be removed from study when any of the following criteria apply:

- Lost to follow-up
- Withdrawal of consent for data submission
- Death
- Completion of the 12-month follow-up period

The reason for taking a participant off study, and the date the participant was removed, must be documented in the case report form (CRF). In addition, the study team will ensure Off Treatment/Off Study information is updated in OnCore in accordance with DF/HCC policy REGIST-101.

6. DOSING DELAYS/DOSE MODIFICATIONS

If a participant has a difficult time swallowing 15 capsules in one day, then capsule administration may be spaced out over three (3) days (10 capsules per day), instead of the standard dosing over two (2) days (15 capsules per day). This is a standard approach in capsule based FMT for recurrent *C. difficile* colitis, though it is noted that the vast majority of patients, including children and the elderly, are able to take 15 capsules in a single sitting. There will be no dose adjustment for participants unable to take 10 capsules per day. In the case of a dosing delay or dose modification, dosing and assessment schedules will remain unchanged (i.e., dosing day count will continue).

Administration of the capsules with applesauce or pudding rather than water is also a standard approach, for subjects who have difficulty swallowing large capsules. The capsules are size 00 (the size of a large pre-natal vitamin). Please note that subjects are fasting around the time of administration to minimize the risk and volume of potential emesis, which is rare. There is no reason food would alter the efficacy of FMT.

